# **Statement of Compliance**

The trial will be carried out in accordance with International Council for Harmonisation of Technical Requirements for Pharmaceuticals for Human Use (ICH) Good Clinical Practice (GCP) and the following:

• United States Code of Federal Regulations (CFR) applicable to clinical studies (45 CFR Part 46, 21 CFR Part 50, 21 CFR Part 56, 21 CFR Part 312, and/or 21 CFR Part 812)

NIH-funded investigators and clinical trial site staff who are responsible for the conduct, management, or oversight of NIH-funded clinical trials have completed Human Subjects Protection and ICH GCP Training.

The protocol, informed consent form(s), recruitment materials, and all participant materials will be submitted to the Institutional Review Board (IRB) for review and approval. Approval of both the protocol and the consent form must be obtained before any participant is enrolled. Any amendment to the protocol will require review and approval by the IRB before the changes are implemented to the study. In addition, all changes to the consent form will be IRB-approved; an IRB determination will be made regarding whether a new consent needs to be obtained from participants who provided consent using a previously approved consent form.

# List of Abbreviations

AE	Adverse event/adverse experience
AR	Adverse reaction
BMI	Body Mass Index
CBC	Complete Blood Count
CC	Clinical Center
CFR	Code of Federal Regulations
CRIMSON	Clinical Research Information Management System of the NIAID
CSO	Clinical Safety Office
ECG	Electrocardiogram
GC	Glucocorticoid
GCP	Good Clinical Practice
GRE	Glucocorticoid Response Element
HAV	Hepatitis A virus
HBsAg	Hepatitis B surface antigen
HCV	Hepatitis C virus
HRPP	Human Research Protection Program
ICH	International Council for Harmonisation of Technical Requirements for
	Pharmaceuticals for Human Use
IND	Investigational new drug
iPS	Induced Pluripotent Stem Cells
IRB	Institutional Review Board
NIAID	National Institute of Allergy and Infectious Diseases
NIAMS	National Institute of Arthritis and Musculoskeletal and Skin Diseases
NIH	National Institutes of Health
NK	Natural Killer (immune cells)
OCRPRO	Office of Clinical Research Policy and Regulatory Operations
OHRP	Office for Human Research Protections
PBMC	Peripheral Blood Mononuclear Cells
RNAi	RNA interference
SAE	Serious adverse event/serious adverse experience
SAR	Suspected adverse reaction
siRNA	Small Interfering RNA
SUSAR	Serious and unexpected suspected adverse reaction
UP	Unanticipated Problem
UPnonAE	Unanticipated Problem that is not an Adverse Event

# **Protocol Summary**

Full Title:	Genomic Response of Human Immune and Non-Immune Cells to Glucocorticoids
Short Title:	Genomic response to GCs
Conducted by:	Systemic Autoimmunity Branch, NIAMS, NIH
Principal Investigator:	[name].
Sample Size:	N=50 maximum. The required sample size will be determined by an adaptive study design after an initial recruitment of 20 subjects
Accrual Ceiling:	60
Study Population:	Healthy volunteers ages 18-64 years
Accrual Period:	60 months
Study Design:	This is a study of glucocorticoid action at the genomic level. Healthy volunteers will undergo baseline blood collection, then receive a single intravenous dose of 250 mg of methylprednisolone. Blood will be collected in one of two regimens: 1 and 2 hours or 2 and 4 hours after the start of the infusion. A skin punch biopsy may be obtained before healthy volunteers receive IV methylprednisolone. If so, topical methylprednisolone will be applied to a limited area of skin, contralateral to the site of the initial skin biopsy, and an additional skin biopsy will be obtained (from the area of topical methylprednisolone application) at the 4-hour time point. Individual participation requires 2 visits to the NIH Clinical Center (CC) and 2 follow-up calls. Total participation time is 1-5 weeks.
	Blood samples will be processed for isolation of hematopoietic cell sub-populations (e.g., neutrophils, B cells, CD4+ T cells, CD8+ T cells, monocytes, and natural killer [NK] cells). Laboratory studies will be performed in the purified cells, with the goal of understanding the human response to glucocorticoids in vivo at the level of RNA (e.g., RNA sequencing, small-RNA-sequencing, real-time PCR), DNA (e.g., ChIP-seq, methylation analysis, DNA sequencing, genotyping), and protein (e.g., flow cytometry, mass spectrometry). At each time point, plasma methylprednisolone levels will be measured and flow cytometry for standard lineage markers will be performed. Skin biopsies will be subjected to RNA

	isolation for RNA sequencing and small-RNA sequencing. A fragment of each skin biopsy will undergo fibroblast isolation and culture for in vitro exposure to glucocorticoids and for the generation of induced pluripotent stem (iPS) cells	
Study Duration:	Start Date: October 2016; End Date: October 2022	
Primary Objective:	To elucidate fundamental differences in the genomic response of immune and non-immune cells to glucocorticoids	
Primary Endpoint:	A list of human genes and non-coding RNAs that are differentiall expressed and regulated in response to glucocorticoids between immune and non-immune cells	
Secondary Objective:	To identify potential targets for small-molecule or nanoparticle- facilitated RNA interference interventions that reproduce the therapeutic action of glucocorticoids while avoiding harmful effects	
Secondary Endpoints:	
 
A list of protein-coding and non-coding transcripts, their corresponding proteins, and the molecular pathways representing the best candidates for targeted therapeutic alternatives to glucocorticoids
 
Validation of the targets identified by functional studies
 
	

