#### 1.3 Choice of a Glucocorticoid and Routes of Administration

Chemical modifications to the 21-carbon corticosteroid backbone (e.g. introduction of a carbon 1-2 double bond, methylation at carbon 6, fluorination at carbon 9), have led to the diverse set of glucocorticoids that is currently available for clinical use. These modifications have mostly altered the pharmacokinetic properties of the drugs, and the relative proportion of mineralocorticoid and glucocorticoid activity, but they do not appear to have significantly altered the mechanism of action or the side effect profile of glucocorticoids. Therefore, the choice of a specific glucocorticoid for our study was based on the frequency of its use in clinical practice, the availability of reports of safe use in studies of healthy human volunteers, and the availability of an intravenous formulation (to reduce potential inter-individual variation in rates of absorption). Methylprednisolone is widely used in clinical practice, with indications in the management of diverse conditions including dermatomyositis (13), lupus nephritis (14), acute asthma exacerbations (15), and relapses of multiple sclerosis (16). Intravenous methylprednisolone has been used in multiple studies of healthy volunteers since the early 1970s (17-19), without reports of serious adverse events (SAEs) in those studies. Sodium succinate and phosphate esters are available for intravenous use. Therefore, we have identified methylprednisolone sodium succinate as the glucocorticoid of choice for our study. Because our study involves a comparison of the effect of glucocorticoids in immune and non-immune cells, in addition to blood we will serially sample a non-hematopoietic tissue. Skin is composed mostly of non-hematopoietic cells and is easily accessible, so we have selected the skin as a nonhematopoietic tissue for sampling. It is unclear from existing literature whether the concentrations of methylprednisolone in skin after intravenous administration are sufficient to induce gene expression changes after short-term administration. However, high concentrations of methylprednisolone in the skin can be achieved with topical administration. Although topical methylprednisolone is widely used in clinical practice around the world, an IND application will be required for topical methylprednisolone use in our study given that topical methylprednisolone is not currently marketed in the United States.

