# 2 Study Objectives and Endpoints

**Primary Objective:** To elucidate fundamental differences in the genomic response of immune and non-immune cells to glucocorticoids

**Primary Endpoint:** A list of human genes and non-coding RNAs that are differentially expressed and regulated in response to glucocorticoids between immune and non-immune cells

**Secondary Objective:** To identify potential targets for small-molecule or nanoparticle-facilitated-RNAi interventions that reproduce the therapeutic action of glucocorticoids while avoiding harmful effects

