# 4 Study Population

# 4.1 Recruitment Plan

Healthy volunteers (N=50 maximum) may be recruited through the NIH Clinical Research Volunteer Program, the Patient Recruitment and Public Liaison Office, or through the posting of advertisements. All flyers and advertisements will be submitted to the NIH IRB for approval.

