# 6.2 Infusion visit (Day 0)

- Targeted physical exam
- Vital signs on first encounter, every 30 minutes from the time of infusion until the time of collection of the four-hour blood sample, and discharge.
- Serum pregnancy test (for volunteers capable of becoming pregnant). For volunteers screened within the past 24 hours, the test will not be repeated.
- Interim medical history and medication review
- Pre-infusion blood draw (for analyses listed in Table 2)
- Optional: Pre-infusion skin biopsy from one arm
- Optional: Application of topical methylprednisolone to the contralateral arm
- Intravenous infusion of methylprednisolone sodium succinate (30 minutes)
- Nursing staff will monitor study subjects for the presence of behavioral abnormalities (altered mood, hyperactivity, disorientation, psychosis)
- Blood draws at 1 and 2 hours or 2 and 4 hours (+/-10 minutes) after the start of infusion (for analyses listed in Table 2)
- Optional: Skin biopsy (at the site where topical methylprednisolone was applied) 4 hours after the start of infusion

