# 14 Statistical Considerations

# **Definition of the Study Endpoints**

- The primary endpoint of this study is a set of lists of human genes and non-coding RNAs (small RNAs and lncRNAs) that are differentially expressed in vivo after a glucocorticoid stimulus in each of six immune cell types (B cells, CD4+ T cells CD8+ T cells, NK cells, neutrophils, and monocytes) and one non-immune tissue (skin).
- The secondary endpoint is a list of the genes and molecular pathways that represent the best candidates for targeted therapeutic alternatives to glucocorticoids.

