despite technical difficulties (notably hemolysis), and the use of hydrocortisone (which is approximately five times less potent than methylprednisolone, the glucocorticoid we plan to use in our study). In addition, the data from the study by Olnes et al. used bulk PBMCs, which are likely to give a more variable expression signal than the purified cell sub-types that we plan to employ in our study. Based on this information, we estimate that an initial recruitment of at least 20 subjects is likely to reveal the changes in gene expression over time that our study aims to define in individual cell sub-types. We propose an adaptive study design, in which we will recruit an initial cohort of 20 subjects. Based on the observed data from 20 subjects, we will then assess the conditional power that can be obtained with up to 30 additional subjects. We will also perform a bootstrap procedure, sampling with replacement up to 50 units from the 20 observed subjects, to evaluate the improvement in gene detection. For example, if the number of genes that can be detected reaches a plateau after 30 subjects, we will stop at that number. However, if the number of detected genes is seen to rise with a sample size of 30, but the pathways and the biological interpretation of the data remain unchanged, additional subjects will be unlikely to change the outcome of the study and no further recruitment will be pursued. Due to the adaptive sample size determination, we will use a nominal significance level  $\alpha < 0.05$ .

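### The sample size of 20 to 50 counts volunteers and is justified on blood alone; it is not secured for skin, the only in vivo non-immune tissue, because biopsy is optional with no planned number of pairs

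*Combined protocol and SAP*

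**What the plan says.** **The comparison.** Section 2 gives the primary objective as "To elucidate fundamental differences in the genomic response of immune and non-immune cells to glucocorticoids". Section 14, Definition of the Study Endpoints, sets out lists for six immune cell types "and one non-immune tissue (skin"). Section 1.3 explains the choice of skin by this comparison and says that "in addition to blood we will serially sample a non-hematopoietic tissue".

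**The biopsies.** The Protocol Summary, the Précis and Section 3 make the biopsy a possibility, in the Summary's words: "A skin punch biopsy may be obtained before healthy volunteers receive IV methylprednisolone". Section 6.2 lists "Optional: Pre-infusion skin biopsy from one arm" and marks the topical application and the 4-hour biopsy as optional too. Section 7 has the baseline sample taken from a subset of volunteers of unstated size. Section 10 gives payment totals with and without biopsy. No section states a target or minimum number of pairs.

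**The sample size.** The Summary states "N=50 maximum. The required sample size will be determined by an adaptive study design after an initial recruitment of 20 subjects", and Section 4.1 says "Healthy volunteers (N=50 maximum) may be recruited". The Sample Size Justification cites a hydrocortisone pilot in PBMCs with 10 subjects per dose and concludes that "an initial recruitment of at least 20 subjects is likely to reveal the changes in gene expression over time", with reference to individual cell sub-types. It does not mention skin. The interim conditional-power and bootstrap assessments are also described in subjects.

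**Use of the skin data.** Under Differential Expression Analysis, genes and pathways modified in immune cells but not in non-immune cells (skin from this study, plus primary cells studied in vitro) become the top candidates for intervention.

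**The concern.** Every volunteer gives blood, but only those who have both biopsies contribute to the skin list. A reader who sees 20 to 50 beside an immune versus non-immune objective will take it as the size of both sides. Only the blood side has a justification.

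A small skin sample does more than shorten the skin list. The selection rule treats failure to reach 5% FDR in skin as evidence of no response there. Low power in skin therefore moves genes that respond in both tissues onto the immune-only list, which is the list meant to guide therapies that spare non-immune tissue. The interim decision, as described, could close recruitment on a plateau in blood while the skin list is still unstable.

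**Working it through.** **1. The plan's own figure.** 20 initial + up to 30 additional = 50, which agrees with the stated maximum. Nothing further can be reproduced: the plan says standard calculations are not appropriate and gives no power, SD or design effect.

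**2. Skin pairs that the plan yields.** Expected pairs = volunteers × uptake. Uptake is an assumption, since the documents give none.

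| Uptake of both biopsies | Pairs from 20 | Pairs from 50 | Volunteers for 20 pairs |
|---|---|---|---|
| 25% | 5 | 12.5 | 20/0.25 = 80 |
| 50% | 10 | 25 | 20/0.50 = 40 |
| 75% | 15 | 37.5 | 20/0.75 ≈ 27 |
| 100% | 20 | 50 | 20 |

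**3. Power in skin.** The assumptions, none of them protocol design figures, are:
- true change 0.75 log2;
- SD of the within-person log2 change 0.6, or 0.4;
- per-gene threshold 0.05 × 600/15,000 = 0.002, where 600 is about the pilot's higher-dose gene count in PBMCs and 15,000 tested transcripts is assumed.

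Power comes from the noncentral t with n − 1 degrees of freedom and noncentrality (0.75/SD) × √n. The ratio 0.75/SD is 1.25 at SD 0.6 and 1.875 at SD 0.4.

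| Skin pairs | Power, SD 0.6 | Power, SD 0.4 |
|---|---|---|
| 5 | 6% | 17% |
| 10 | 44% | 89% |
| 15 | 82% | about 100% |
| 20 | 96% | about 100% |

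For a 1.0 log2 change at SD 0.6 the figures are 12, 78, 99 and about 100%.

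**4. From power to false candidates.** Take a gene that changes by 0.75 log2 in both tissues and has been detected in an immune cell type. If the errors in the two tissues are independent, it is labelled immune-only with probability 1 − (power in skin). At SD 0.6 this is 94, 56, 18 and 4% with 5, 10, 15 and 20 pairs. At SD 0.4 it is 83% with 5 pairs, 11% with 10, and close to zero with 15 or 20.

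**5. Sensitivity to the test.** The planned software, Cuffdiff for RNA-seq and DESeq for small RNA, shares variance information across transcripts, so a per-gene t-test is pessimistic at small n. Treating the variance as known gives an upper bound, Φ((0.75/SD)√n − 3.09). At SD 0.6:
- 5 pairs: Φ(2.80 − 3.09) = 38%
- 10 pairs: Φ(3.95 − 3.09) = 81%
- 20 pairs: Φ(5.59 − 3.09) = 99%

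At SD 0.4 with 5 pairs it is Φ(4.19 − 3.09) = 86%.

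**6. The blood side at the matching time.** The second biopsy is at 4 hours. Blood is drawn either at 1 and 2 hours or at 2 and 4 hours, and the split is not stated. All volunteers have a 2-hour sample, but only those on the second regimen have a 4-hour one, so the blood n at the time of the skin sample is also unstated.

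**The case against.** The strongest reply is that the plan promises less than a critic may suppose. Four stronger readings are tempting, and the documents support none of them.

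- *The plan claims a size for the immune versus skin comparison, and the claim fails.* It makes no such claim. Its statement about 20 subjects concerns blood cell sub-types. If every volunteer accepted biopsy, the skin n would equal the volunteer n.
- *The study could finish with no skin data.* No rule forbids it, but Section 7 plans a baseline biopsy in part of the cohort, so zero pairs strains the text. The realistic risk is few pairs.
- *Section 1.3 contradicts the optional biopsy.* It is a statement about the study, and it is compatible with each volunteer's choice.
- *The protocol's own numbers, 20 subjects or the pilot's 10 per dose, can serve as skin thresholds.* Both come from blood. Twenty pairs would need about 40 volunteers at 50% uptake and about 80 at 25%, the latter above the maximum. Ten pairs give only 44% power in the SD 0.6 case. Nor can 20 to 50 be called the blood size without qualification, because it need not hold at 4 hours.

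Three further points carry some weight. The in vitro cells also count as non-immune when candidates are selected, but the primary endpoint is defined in vivo, so they cannot supply the skin list. The interim rule asks whether the biological interpretation would change, so a sparse skin list might prompt recruitment, but nothing requires skin to be examined. Finally, the power figures depend on an assumed SD and on a test that the plan does not use, and with a small SD and well-shared variance even five pairs might do.

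**Conclusion.** The concern stands in this form: the stated size is justified for blood cell sub-types and is not secured for skin, while the candidate rule depends on what is not detected in skin.

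The size of the problem is uncertain because uptake and SD are unknown. For a 0.75 log2 change under the t-test assumptions, five pairs are weak at either SD (6% or 17%). Ten range from poor to adequate (44% to 89%), and 20 are good at either SD (96% or more). Sharing variance across transcripts would raise these figures. The direction needs none of these assumptions: with other things equal, fewer skin pairs mean more responses missed in skin and more false immune-only genes. The plan should be changed on this point, but the lapse does not affect the six blood lists.

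**What to change.** 1. **State the size by tissue and time point** in the Protocol Summary and Section 14. Skin n is the number of volunteers with both biopsies. Blood n at 4 hours is the number on the 2- and 4-hour regimen; at 2 hours it is all volunteers sampled.
2. **Run the interim assessment on skin too.** Apply the conditional-power and bootstrap steps to the skin pairs as well as to each blood cell type. Do not stop on blood results alone while the skin list is still changing, within the existing maximum of 50.
3. **Change what counts as immune-only.** Report skin n beside every statement that a gene does not respond in skin. Use the immune-only label only when the skin estimate and its interval exclude a response of the size seen in immune cells; otherwise record the gene as undetermined in skin. At SD 0.6, the 95% half-width is 2.776 × 0.6/√5 = 0.74 log2 with 5 pairs and 2.093 × 0.6/√20 = 0.28 with 20, so the rule adapts to the pairs obtained without a fixed cut-off.

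Biopsy stays optional and no procedure is added. The costs are a less favourable stated size for skin, possibly a shorter candidate list, and possibly continued recruitment, with its infusions and sequencing, up to the approved maximum.

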# Précis

Glucocorticoids are among the most frequently prescribed immunosuppressive and antiinflammatory medications worldwide. Long-term use, however, is complicated by serious nonimmunologic side effects. Ongoing in vitro experiments with human primary cells in our laboratory suggest that there are indeed fundamental differences in the genomic response of immune and non-immune cells to glucocorticoids. These and other aspects of drug action at the genomic level have not been completely characterized. This study will attempt to generate a list of human genes and non-coding RNAs that are differentially expressed and regulated in response to glucocorticoids between immune and non-immune cells. These data will be used to identify transcripts, their corresponding proteins, and the molecular pathways that are best candidates for targeted intervention. Potential targets could be validated with small interfering RNA (siRNA) libraries, with the long-term goal of developing small-molecule or nanoparticle-facilitated RNA interference (RNAi) interventions that reproduce the therapeutic action of glucocorticoids in immune cells while avoiding their harmful side effects on other tissues.

[figure not shown]
Healthy volunteers will undergo baseline blood collection prior to receiving a single intravenous dose of 250 milligrams of methylprednisolone sodium succinate. Blood will be collected in one of two regimens: 1 and 2 hours or 2 and 4 hours after the start of the infusion. A skin punch biopsy may be obtained before healthy volunteers receive IV methylprednisolone. If so, topical methylprednisolone will be applied to a limited area of skin, contralateral to the site of the baseline skin biopsy, and an additional skin biopsy will be obtained 4 hours after drug administration, from the area where topical methylprednisolone was applied. Follow-up phone calls 1 and 5 days after discharge will document any adverse effects related to the drug or skin biopsy. Total length of individual study participation is 1-5 weeks.

Blood samples will be processed for isolation of hematopoietic cell sub-populations (e.g. neutrophils, B cells, CD4+ T cells, CD8+ T cells, monocytes, and natural killer [NK] cells). Laboratory studies will be performed in the purified cells, with the goal of understanding the human response to glucocorticoids in vivo at the level of RNA (e.g., RNA sequencing, small-RNA-sequencing, real-time PCR), DNA (e.g., ChIP-seq, methylation analysis, DNA sequencing, genotyping), and protein (e.g., flow cytometry, mass spectrometry). At each time point, serum methylprednisolone levels will be measured and flow cytometry for standard lineage markers will be performed. Skin biopsies will be subjected to RNA isolation for RNA sequencing and small-RNA sequencing. A fragment of each skin biopsy will undergo fibroblast isolation and culture for in vitro exposure to glucocorticoids and for the generation of induced pluripotent stem (iPS) cells.

